6.2.10. Hemophilia Joint Health Score (HJHS)

The HJHS total score at different time points will be compared to the baseline using a paired t-test.

The number of participants (n), mean, median, standard deviation, Q1, Q3, min, max, and the 95% CI of mean for the observed value and change from baseline, as well as the p-value from the paired t-test for change from baseline, will be presented by visit based on the ‘Dosed’ population.

6.2.11. PRO Assessments

Haem-A-QoL and HAL endpoints will be analyzed as continuous or categorical variables according to the data type. For each visit, the observed value post PF-07055480 infusion will be compared to the baseline using paired t-test for continuous variables.

For the primary analysis, Haem-A-QoL Physical Health domain score and HAL Complex Lower Extremity Activities domain score at Month 12 are included in the gatekeeping sequence for hypothesis testing. To avoid missing data in the assessment at Month 12, HJHS/PRO data collected at unscheduled visits during Month 12 through Month 15 (i.e., during Week 51 through Week 65) will be included for Month 12 assessment.

6.2.11.1. Haem-A-QoL

The Haem-A-QoL assesses health-related quality of life (HRQoL) in adult patients ≥ 17 years of age with haemophilia. It included 46 items contributing to 10 HRQoL domains, as depicted in the table below. All Haem-A-QoL items are based on a 5-point Likert-type scale (1 = never, 2 = rarely, 3 = sometimes, 4 = often and 5 = all the time). A 'Not applicable' response option is also available for the domains of 'Sports and Leisure', 'Work and School', and 'Family Planning' when the question may not apply to the participant. Some of the items need to be re-coded.

The items prompt the responder to consider life in the last four weeks ('four-week recall'). Scoring is performed by averaging the non-missing item responses for each domain, and then rescaled to be on 0 to 100, with lower scores representing higher quality of life. The total score is directly averaged across the 46 items values and then rescaled on zero to 100.

The 10 domain scores of health-related quality of life as well as the total score will be assessed and compared to the corresponding baseline using paired t-test. The Physical Health domain is considered the main endpoint of this instrument. A domain score can be calculated if $\geq 50\%$ of that domain's items have been answered.

The number of participants with non-missing observations (n), mean, median, standard deviation, Q1, Q3, min, max, and the 95% CI of mean for the observed value and change from baseline, as well as the p-value from the paired t-test for change from baseline, will be provided separately for domains and total score by visit based on the 'Dosed' population.

6.2.11.2. Hemophilia Activities List (HAL, v2)

The 7 domains of the activities HALs and three component scores can be calculated, and each will be compared to the corresponding baseline using a paired t-test. Each domain or component, or the total, has a required minimum number of valid responses or the score is set to missing. An implication of the 'minimum number of valid responses' is that there is an acceptable amount of missing data where the scores (domains, components, and total; raw and normalized) can still be calculated. Complex activities involving the Lower Extremities is considered as the main endpoint for this instrument.

The number of participants (n), mean, median, standard deviation, Q1, Q3, min, max, and the 95% CI of mean for the observed value after normalization and change from baseline, as well as the p-value from the paired t-test for change from baseline, will be provided by visit based on the 'Dosed' population.

6.3. Other Endpoints

6.3.1. Additional PRO Assessments

6.3.1.1. Hemophilia Life Impacts Questionnaire (HLIQ)

The HLIQ is a 9-item assessment of life impacts associated with living with and treating hemophilia. These 9 individual item scores will be compared to the corresponding baseline using paired t-test.

The number of participants, counts and percent by response to individual items will be provided by visit based on the ‘Dosed’ population.

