3.3.1.1. Hemophilia Life Impacts Questionnaire (HLIQ)

The HLIQ is a 9-item assessment of life impacts associated with living with and treating hemophilia. The HLIQ employs a 'past week' recall period. Four items are assessed on a 5-point, ordinal, verbal rating scale scored from 0 to 4, while 4 items are gated such that responding 'yes' branches to a 5-point, ordinal verbal rating scale and responding 'no' branches to a reason for not participating in the activity (i.e., due to hemophilia or due to

other reasons). One item is assessed on a 4-point, ordinal, verbal rating scale scored from 0 to 3. Higher scores on the verbal rating scales indicate greater impact due to living with or treating hemophilia.

HLIQ baseline is the latest evaluation prior to PF-07055480 infusion, which is measured during the baseline period of this study.

3.3.1.2. Patient Global Impression of Severity (PGIS) and Patient Global Impression of Change (PGIC)

The PGIS-Physical Health (PH) is a single item assessment of the participant's overall impression of severity of physical health over the past 7 days. The response scale is a 4-point categorical rating scale ranging from 'none' to 'severe'.

The PGIS-Physical Functioning (PF) is a single item assessment of the participant's overall impression of severity of physical functioning over the past 7 days. The response scale is a 4-point categorical rating scale ranging from 'none' to 'severe'.

The PGIS-Hemophilia (H) is a single item assessment of the participant's overall impression of severity of life interference with hemophilia over the past 7 days. The response scale is a 4-point categorical rating scale ranging from 'none' to 'severe'.

The PGIC-PH is a single item assessment of the participant's overall impression of change in their physical health since receiving gene therapy. The response scale is a 5-point categorical rating centered around 'no change' with 2 grades of improvement and 2 grades of worsening.

The PGIC-PF is a single item assessment of the participant's overall impression of change in their physical functioning since receiving gene therapy. The response scale is a 5-point categorical rating centered around 'no change' with 2 grades of improvement and 2 grades of worsening.

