Joint status as assessed by X-ray in Pettersson scale: change from baseline in total score, scores at specific joints, and scores at	Final analysis: Tertiary/Exploratory	Joint x-ray substudy	No imputation for missing data.	Descriptive summary, 95% CI of mean for the observed value and

Endpoint	Analysis Type	Population	Data Inclusion and Rules for Handling Intercurrent Events and Missing Data	Analysis
target joints at Week 156 (Year 3) and Week 260 (Year 5 or Early Discontinuation Visit)				change from baseline, and p-value from the paired t-test.
Joint status as assessed by ultrasound based on HEAD-US scoring at Week 24, Week 52 or Early Discontinuation Visit	Primary analysis: Tertiary/Exploratory	Evaluable population in the ultrasound substudy	No imputation for missing data.	Counts and percent for individual items. Total score for each joint will be summarized by visit with descriptive statistics and 95% CI of mean for the observed value and change from baseline.
PGIS and PGIC by visit	Primary analysis and Final analysis: Tertiary/Exploratory	Dosed	No imputation for missing data.	Counts and percent.
HLIQ by visit	Primary analysis and Final analysis: Tertiary/Exploratory	Dosed	No imputation for missing data.	Counts and percent by response to individual items.
Change from baseline in EQ-5D-5L Index score and VAS score by visit	Primary analysis and Final analysis: Tertiary/Exploratory	Dosed	No imputation for missing data.	Descriptive summary, 95% CI of mean for the observed value and change from baseline, and p-value from the paired t-test.

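### SAP 6.3.1.1 orders paired t-tests on all nine HLIQ items that its own output list and Appendix 2 omit, and four of those items have no stated score for a 'no' answer

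*SAP*

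**What the plan says.** SAP Section 6.3.1.1 gives the HLIQ two analyses. The first is inferential: "These 9 individual item scores will be compared to the corresponding baseline using paired t-test". The second is descriptive, on the Dosed population: "The number of participants, counts and percent by response to individual items will be provided by visit". The HLIQ row of SAP Appendix 2 has only the second: "Counts and percent by response to individual items". It also says that missing data are not imputed.

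SAP Section 3.3.1.1 describes the instrument, and Protocol Section 8.1.4.3 agrees. Four items are rated directly from 0 to 4 and one from 0 to 3. The other four are gated. A 'yes' opens a 5-point rating. A 'no' "branches to a reason for not participating in the activity", the options being hemophilia or something else. The meaning of a score is tied to the rating scales alone: "Higher scores on the verbal rating scales indicate greater impact due to living with or treating hemophilia".

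SAP Section 5.3 rules out imputation unless Section 3 or Section 6 specifies it. Neither does so for the HLIQ.

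**The concern.** There are two linked problems.

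1. **Internal conflict.** A programmer working from Section 6.3.1.1 would produce nine tests per postbaseline visit. One working from Appendix 2 would produce none.
2. **Gated items.** If the tests are run, a 'no' at baseline or at the later visit leaves no pair for that item. The exclusion depends on the response itself. Not taking part in an activity because of hemophilia is a life impact, so moving into or out of that answer is a change the questionnaire could be expected to register.

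At stake is the exploratory objective in Protocol Section 3 and SAP Table 2, which calls for comparing HLIQ responses before and after infusion. For the gated items, the test would describe change only among people doing the activity at both times, under a heading that suggests all dosed participants.

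**Working it through.** The documents give no sample size, power or alpha for the HLIQ, so there is no design figure to reproduce. The check is a comparison of the text plus simple counting.

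**Step 1: is the t-test planned?**

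| Place in SAP | HLIQ | Other PROs |
|---|---|---|
| Section 6, method | Paired t-test, all nine items | Paired t-test |
| Section 6, output list | Counts and percent only | Means, CI and paired t-test p-value (6.2.11.1, 6.2.11.2; EQ-5D-5L Index and VAS in 6.3.1.3) |
| Appendix 2 | Counts and percent only | Paired t-test p-value named for Haem-A-QoL, HAL and EQ-5D-5L |

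Appendix 2 names the test for the other instruments, so its absence from the HLIQ row is not mere abbreviation. One sentence stands against two other places.

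**Step 2: how many items are affected?** 4 directly rated (0 to 4) + 4 gated + 1 directly rated (0 to 3) = 9. The gating problem affects 4 of the 9 tests.

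**Step 3: what happens to a 'no'?** No value is assigned to it and no imputation is specified. The other PROs have rules for unanswered or missing items: Haem-A-QoL needs at least 50% of a domain's items, HAL needs a minimum number of valid responses, and EQ-5D-5L scores become missing. The HLIQ has no such rule, so as written the pair is lost.

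**Step 4: how many pairs could be lost?** The documents give no 'no' rates, so these are assumptions. Take N = 50, the minimum number of dosed participants for the primary analysis. Let q0 be the share answering 'no' at baseline and q1 the share at the visit.

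- Most pairs possible: N × (1 − q0)
- Pairs if the two answers are independent: N × (1 − q0) × (1 − q1)

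| q0 | Most pairs | Pairs with independent 'no' at visit |
|---|---|---|
| 10% | 50 × 0.9 = 45 | q1 = 10%: 45 × 0.9 = 40.5 |
| 20% | 50 × 0.8 = 40 | q1 = 20%: 40 × 0.8 = 32 |
| 30% | 50 × 0.7 = 35 | q1 = 20%: 35 × 0.8 = 28 |

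**Step 5: which way could the bias go?** For illustration only, score the gated ratings 0 to 4 like the directly rated items and code 'no, due to hemophilia' as 4. Neither choice is in the documents.

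- *Gains omitted.* 40 participants are unchanged and 10 move from 'no, due to hemophilia' to 'yes' with score 1. With the 10 dropped, the mean change is 0.0. With the code of 4 it is (40 × 0 + 10 × (1 − 4)) / 50 = −0.6.
- *Losses omitted.* 40 improve by 0.5 and 10 move from score 2 to 'no, due to hemophilia'. With the 10 dropped, the mean change is −0.5. With the code of 4 it is (40 × (−0.5) + 10 × (4 − 2)) / 50 = 0.0.

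The first case hides a benefit. The second shows a benefit that the code would cancel.

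**Step 6: do the planned counts fill the gap?** Only in part. Counts by visit can show how many gave each answer at each visit. They do not show who moved: ten 'no' answers at both visits could be the same ten people or twenty different ones.

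**The case against.** The strongest reply is that the t-test sentence is probably a leftover. The SAP version history (Table 1, Version 3) records a move to counts and percentages for each HLIQ question, with no total score, and both output descriptions fit that. On this view no biased test would be reported. That is plausible and makes the conflict the firmer half of the point, but the sentence is still in the current SAP and should be removed.

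A second reply is that the absence of a score for 'no' is inferred. Section 6.3.1.1 speaks of nine item scores, and the version history mentions HLIQ scoring and a questionnaire appendix that are no longer included. A scoring manual outside these documents could assign a value. This stands as a limit: what can be said is that the protocol and SAP assign none and cite no HLIQ scoring source.

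A third reply is that counts by response can already separate the two kinds of 'no', and that SAP Section 6.3.1.2 sends interpretation of HLIQ change to a separate analysis plan reported outside the CSR. Both are true. Within-person movement on the gated items is still not among the planned outputs.

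A reader might go further and infer that the test discards the most severely affected participants, or that it understates benefit by a definite amount. The documents do not support either. They say a participant is not taking part in an activity, not that he is unable to or is among the worst affected. They give no response rates and no code for 'no', and Step 5 shows bias in both directions.

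**Conclusion.** The point holds as an internal contradiction with a secondary analysis flaw. Section 6.3.1.1 conflicts with its own output list and with Appendix 2 on whether the nine tests are done. If they are done as written, the four gated items are tested only in participants answering 'yes' at both visits.

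This assumes that no scoring rule outside the documents gives 'no' a value. The size of any bias cannot be derived: the pair counts and mean changes above show the mechanism under assumed inputs and are not estimates. The consequence is minor. The HLIQ is a tertiary/exploratory endpoint, is absent from the gatekeeping sequence in SAP Table 8, and bears on no alpha, sample size or decision rule.

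**What to change.** 1. Delete the paired t-test sentence in SAP Section 6.3.1.1 for all nine items, so that the section agrees with Appendix 2. Deleting it for the gated items alone would leave the conflict in place for the other five.
2. For the four gated items, add a baseline-to-visit shift table that shows the rating categories together with 'No, due to hemophilia' and 'No, other reasons' as two separate categories. Add the same output to the HLIQ row of Appendix 2. The table gives a before-and-after comparison without requiring a numeric code for 'no'.

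The cost is SAP wording and one changed exploratory table. Data collection is unaffected.

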6.3.1.2. PGIS and PGIC

The PGIS-PH, PGIC-PH, PGIS-PF, PGIC-PF, PGIS-H and PGIC-H global items are collected to enable an anchor-based method for interpreting changes in the Haem-A-QoL (-PH), HAL (-PF) and HLIQ (-H), respectively. These interpretation analyses will be described in a separate analysis plan. The PRO interpretation results will be reported separately from the CSR.

For the CSR, data of PGIC and PGIS endpoints will be summarized with counts (%) by response for each visit based on the ‘Dosed’ population.

6.3.1.3. EQ-5D-5L

Each of the 5 dimensions (i.e., ‘Mobility’, ‘Self-care’, ‘Usual activities’, ‘Pain/discomfort’, and ‘Anxiety/depression’) in the EQ-5D questionnaire is assessed with 5 levels of perceived problems:

Level	Description	Score
Level 1	No problem	1
Level 2	Slight problems	2
Level 3	Moderate problems	3
Level 4	Severe problems	4
Level 5	Extreme problems	5

A health state is defined by the combination of one level from each of the 5 dimensions. There is a total of 3125 possible health states. For example, state 11111 indicates no problems on any of the 5 dimensions, while state 12345 indicates no problem with mobility, slight problems with washing or dressing, moderate problems with doing usual activities, severe pain or discomfort and extreme anxiety or depression.

The Index score (total score) of EQ-5D-5L will be obtained, according to the health state defined by the 5-dimension scores, from the Crosswalk Index value calculator and table lookup document under the target country population. For the study CSR, weights under the United States population will be used to obtain the Index score.

Scores of the 5 dimensions will be summarized with counts and percent for scores in each

dimension by visit.

The number of participants with non-missing observations (n), mean, median, standard deviation, Q1, Q3, min, max, and the 95% CI of mean for the observed value and change from baseline, as well as the p-value from the paired t-test for change from baseline, will be provided for the Index score and VAS score by visit based on the 'Dosed' population.

6.3.2. Vector Shedding and Infectivity

Descriptive summaries of shedding vector levels in PBMC, saliva, urine, semen, and plasma will be provided, including a summary of peak vector levels, time to peak vector levels and time to undetectable/negative vector. Vector levels that are reported as below the lower limit of quantification (<LLoQ) by the bioanalytical laboratory are considered as negative. A peak level is defined for each participant as the highest vector level collected prior to the first set of 3 consecutive negative results in a given specimen type. If multiple assessments are collected for a study visit, the highest value will be included in the summary as a conservative approach. Number and percentage of participants who achieved 3 consecutive negative results will be reported for each specimen. Number and percentage of participants <LLoQ at each visit will also be summarized in the table.

The following time to event endpoints will be derived using the first set of three consecutive negative results in a given specimen type. Time to undetectable/negative vector (defined as time to first of three consecutive negative results), time to last of three consecutive negative results, and time to the last positive prior to three consecutive negatives will be summarized. The number of participants (n), mean, median, standard deviation, Q1, Q3, min, and max will be presented by visit in summary tables. A median plot of vector shedding over time will be generated with specimen types differentiated by different color/symbols. A box and whisker plot of vector levels over time will be generated for each specimen.

The summary table will be generated for the 'Vector Shedding Substudy' population (described in [Section 3.3.2](#)) and the 'Dosed' population. 'Vector Shedding' subgroup (optional substudy) will have more extensive vector shedding analysis performed on their specimens to further characterize the kinetics of vector shedding. The data of this subgroup will be separately presented.

Samples from the substudy will also be assessed by DNase digestion method for saliva, semen, and urine. Results from both DNase digested and undigested samples will be summarized separately in another table. Individual plots of vector shedding over time will be generated for all subjects and the figures will be presented in log-linear scales. In the individual plots, <LLoQ values will be imputed as one half of the LLoQ value for plotting purposes. The plot will be paged by participant and paneled by specimen type, and results from both lab methods will be plotted on the same figure, differentiated by color/symbols. Results from the two methods will be presented side by side in a data listing.

In addition, baseline, demographic characteristics, weight, body mass index, and FVIII activity level data collected for the participants in this substudy will be summarized.

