Vector shedding analysis by PCR and infectivity (CL)		X	X*	Weekly, as needed # Or every 2 weeks past Week 20 Home health/mobile phlebotomy services allowed From Week 34, monthly collection is allowed in the absence of home health/mobile phlebotomy services at a site or country					
 • #Collect plasma, PBMC, saliva, semen, and urine specimens at baseline and every week after study intervention until 3 consecutive specimens test negative for the given specimen type. • #Collection of blood to prepare PBMCs and assess shedding postinfusion will start from Week 20. • Semen samples may be collected at home the night before a clinic or home health/mobile phlebotomy services visit and stored in the participant's freezer until the clinic or home health/mobile phlebotomy services visit. • *Optional vector shedding sub-study (12 participants): additional samples (plasma, PBMC, saliva, semen and urine) will be collected, onsite only, 2 h [± 30 min], 24 h [± 3 h], and 72 h [± 4 h] after completion of the study intervention infusion/IV line flush. • Infectivity will be performed as applicable. Refer to Section 8.5.1 for additional details. 		

Procedures Year 1	Screening Period	Baseline Period	Study Intervention	Week 1-12 (±2 days)	Weeks 13-52 (±1 week)	
 ○ [#] The schedule of assessments should be based on Day 1. ○ *Visit 4/Week 1: The participant is not required to appear onsite. If onsite visit: perform all procedures as specified in the SoA. If not onsite visit: collect only all required laboratory specimens as specified in the SoA. ○ **Day 1: after end of study intervention infusion, 24 h hospitalization is planned. ○ Home health/mobile phlebotomy services may be used for pre-dose LFT blood draw and any time after Study Day 1/Visit 3, as needed (for most biological samples collection). ○ Clinical decisions may be based on local or central laboratory assessments. ○ Refer also to the General Notes at the beginning of the SoA.
Any additional safety tests	Ongoing (as needed)			Additional laboratory testing or procedures may be conducted as deemed clinically necessary by the investigator to ensure the safety of participants.		
Adverse events	Ongoing (including unscheduled visits)			During the short-term monitoring period (up to and including 104 weeks postinfusion) all SAEs and AEs will be collected (Section 8.3.1 and Appendix 3).		

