8.5. Pharmacokinetics

8.5.1. Vector Shedding and Infectivity

Shedding will be assessed by quantitative real time PCR. Samples of plasma, saliva, PBMC, urine, and semen will be collected as specified in the SoA for analysis of vector shedding and infectivity. These samples will be collected as per the instructions provided to the sites to maintain sample integrity for each sample type. Any deviations from that sample handling procedure must be documented and reported to the sponsor.

In the event that a participant is unable to provide any semen for vector shedding over the course of 1 month postinfusion, future attempts to provide semen samples can be stopped provided that 3 consecutive negative PBMC samples are obtained, before no longer being required to follow the restriction within inclusion criteria #6 in [Section 5.1](#).

In the event that samples of plasma, saliva, PBMC, urine, and semen have not yet cleared 20 weeks post infusion, collection can be reduced to every 2 weeks.

Based on preliminary vector shedding data obtained on PBMCs assessed in the ongoing C3731003 study and to limit burden to the participants and collected blood volume, collection of blood to prepare PBMCs and assess shedding post infusion will start from Week 20.

In the event that plasma, saliva, PBMC, urine, and semen have not yet cleared 34 Weeks post infusion, and if home health care service is not available in a country or at a site, collection can be reduced to approximately monthly.

Some participants (n=12), who consent to participate in an optional substudy, are expected to provide additional samples at early timepoints following study intervention (2 h [\pm 30 minutes], 24 h [\pm 3 h], 72 h [\pm 4 h] after completion of study intervention infusion and IV line flush). This subset of samples will also be used for DNase treatment for additional characterization.

If further characterization is needed (eg, unusual shedding result), a functional assay may be done to evaluate the infectivity of the virus. This assay will involve in vitro culture of shed material with a permissive cell line.

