4.1 Overall Design			
9.2 Sample Size Determination			
Section 8.3.10 Immunomodulation Optimization (Presumed T-Cell Activation)	As implemented via the PACL dated 12 September 2022: consolidation and further refinement of the guidance for initiation of corticosteroid treatment to more clearly incorporate considerations about ALT levels, FVIII activity levels along with time from girooctocogene fitelparvovec infusion.	The revisions are for clarity and completeness, to further assist investigators in their decision making. All considerations included in protocol Section 8.3.10 continue to be for guidance only as the decision on whether and when to initiate corticosteroid treatment in a study participant remains with the investigator, based on clinical judgement.	Nonsubstantial
Section 1.3 Schedule of Activities	As implemented via the PACL dated 12 December 2022: Blood collection to prepare PBMCs and assess shedding in this matrix will start from Week 20.	Update made based on preliminary data from the already dosed participants and the observed prolonged clearance time in PBMCs, to limit burden to the participants and collected blood volume. This change will have no impact on the assessment of clearance time in PBMCs. Available data for the already dosed participants will allow assessment of early shedding kinetics and peak related data.	Nonsubstantial
Section 8.5.1 Vector shedding and infectivity			
Section 9.3 Populations for Analyses	Minor clarifications/corrections	Updates made for consistency with SAP	Nonsubstantial

Section # and Name	Description of Change	Brief Rationale	Substantial or Nonsubstantial
Section 9.4.1 Efficacy Analyses			
Section 9.5.1 Data Monitoring Committee (DMC)	Clarifications	Updates made for consistency with the sponsor's protocol template regularly updated to ensure regulatory compliance.	Nonsubstantial
Section 10.1.1 Regulatory and Ethical Considerations			
Section 10.1.4 Data Protection			
Section 10.1.6 Dissemination of Clinical Study Data			
Section 10.1.7 Data Quality Assurance			
Section 10.1.9 Study and Site Start and Closure			
Section 10.1.10 Publication Policy			

This amendment incorporates all revisions to date, including amendments made at the request of country health authorities and IRBs/ECs and any protocol administrative change letter(s). Editorial, grammatical, formatting, and administrative changes were made throughout the document.

Amendment 8 (21 November 2022)

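### SAP 6.3.2 gives vector clearance times no censoring rule, so slow-clearing specimens will look faster at the primary analysis, and it pools PBMC peaks across two sampling schemes

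*SAP*

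**What the plan says.** **Clearance.** SAP 6.3.2 plans descriptive summaries of vector levels for each specimen type, "including a summary of peak vector levels, time to peak vector levels and time to undetectable/negative vector". It then states: "The following time to event endpoints will be derived using the first set of three consecutive negative results in a given specimen type". Three times follow from that run: to its first negative, to its last negative, and to the last positive before it. The next sentence names the statistics: "The number of participants (n), mean, median, standard deviation, Q1, Q3, min, and max will be presented by visit in summary tables". No censoring rule or Kaplan-Meier estimate appears, and nothing says what happens to a participant without such a run. SAP 5.3 leaves missing data unimputed unless an endpoint section says otherwise, and neither SAP 3.3.2 nor 6.3.2 does. The section does add: "Number and percentage of participants who achieved 3 consecutive negative results will be reported for each specimen".

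**Peak.** SAP 6.3.2 has one definition for all specimen types: "A peak level is defined for each participant as the highest vector level collected prior to the first set of 3 consecutive negative results". The tables are produced for the Dosed population and, separately, for the 12-participant shedding substudy.

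**PBMC sampling.** The Year 1 Schedule of Activities says: "Collection of blood to prepare PBMCs and assess shedding postinfusion will start from Week 20". Protocol 8.5.1 agrees: "collection of blood to prepare PBMCs and assess shedding post infusion will start from Week 20". Substudy members also give PBMC samples at 2, 24 and 72 hours. The Amendment 9 entry in Protocol Appendix 10 gives the sponsor's reasoning: "Available data for the already dosed participants will allow assessment of early shedding kinetics and peak related data".

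**The concern.** The SAP itself calls the clearance times time-to-event endpoints, but plans to summarise them as complete measurements. Those with no value at the cutoff are the slowest to clear or the least followed, so leaving them out shortens the mean, median and quartiles.

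Uncleared participants are foreseen. Protocol 8.5.1 makes provision for specimens still positive at Weeks 20 and 34. The Year 2 to 5 schedule continues shedding collection. Amendment 9 refers to prolonged clearance in PBMC. SAP Section 6 describes the primary analysis, which is triggered when at least 50 participants have 15 months of follow-up. The Dosed population may also hold participants with less.

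For PBMC, a later-dosed participant outside the substudy has no post-infusion sample before Week 20. His recorded peak is the highest level from Week 20 on, and his time to peak cannot be shorter than 20 weeks. Averaged with participants sampled weekly from Week 1, these values describe neither group.

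At stake is the accuracy of the trial's description of vector persistence and of PBMC peak levels.

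**Working it through.** The documents state no clearance time, half-life or number of later-dosed participants. There is no figure to reproduce, and the sizes below are illustrations under stated assumptions.

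**1. Clearance, main illustration.** Assumptions:
- Clearance time T = m × exp(0.6 × Z), with Z standard normal and m the true median in weeks.
- Follow-up C is uniform from 15 to 36 months (65 to 157 weeks) at the primary analysis, or 260 weeks at the final analysis.
- A participant contributes a value only if T ≤ C. The reported median is the median of T among those participants.

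| True median (wk) | Cleared, primary | Reported median, primary | Reported median, 260 wk |
|---|---|---|---|
| 20 | 99.5% | 20 | 20 |
| 26 | 98% | 25.7 | 26 |
| 34 | 96% | 33 | 34 |
| 40 | 94% | 38 | 40 |
| 52 | 87% | 47 | 52 |
| 78 | 69% | 61 | 77 |

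The mean is affected more. The true mean is m × exp(0.6²/2) = 1.197m. For m = 78 that is 93 weeks, against a reported mean of 65. Requiring 4 further weeks of follow-up to confirm the three negatives at two-weekly sampling changes the last two primary medians only to 46.6 and 60.3.

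**2. Clearance, other assumptions.** Follow-up is 65 weeks for everyone, sampling is two-weekly, and all three negatives must fall within follow-up.

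| True median (wk) | Exponential: reported (cleared) | Log-normal, sigma 0.5: reported (cleared) |
|---|---|---|
| 20 | 18 (88%) | 20 (99%) |
| 40 | 24 (64%) | 36 (79%) |
| 60 | 26 (50%) | 44 (50%) |
| 80 | 28 (40%) | 48 (28%) |

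The direction is the same throughout. The size depends on the shape of the distribution and on the share not yet cleared.

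**3. PBMC peak.** Assume a true peak at Week 1 and log-linear decay with half-life h weeks. The level first seen at Week 20, as a share of the peak, is 0.5^(19/h):
- h = 2: 0.1% (2.9 log10 too low)
- h = 4: 3.7% (1.4 log10)
- h = 8: 19% (0.7 log10)
- h = 16: 44% (0.4 log10)

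An early peak is itself an assumption for PBMC. Protocol 2.3.1 reports that shedding in the Phase 1/2 study was generally highest in the first couple of weeks, but PBMC is not among the specimens it lists.

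**4. PBMC time to peak.** Suppose a share f of participants is first sampled at Week 20 and the rest peak at 1.5 weeks on average. The pooled mean is 1.5(1 − f) + 20f:
- f = 0.1: 1.35 + 2.00 = 3.35 weeks
- f = 0.3: 1.05 + 6.00 = 7.05 weeks
- f = 0.5: 0.75 + 10.00 = 10.75 weeks

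**5. Opposite direction for PBMC clearance.** A later-dosed participant who cleared PBMC before Week 20 cannot record a negative until Week 20, so his clearance time is too long. The Amendment 9 entry treats clearance assessment as unaffected by the change and describes PBMC clearance as prolonged, which suggests such cases are uncommon.

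**The case against.** **The method is inferred.** The SAP nowhere says that clearance is summarised in cleared participants only. The sentence listing the statistics speaks of presentation by visit, which suits vector levels better than a time with one value per person. This is fair as to wording. It does not rescue the plan: the general rule for continuous endpoints in SAP 5.2.2 gives the same kind of statistics, and a time derived from a run that has not occurred does not exist.

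**Incompleteness will be visible.** The tables give the percentage with three consecutive negatives and the percentage below the quantification limit by visit, and individual plots are planned. These show a reader that data are missing, but they do not correct the median beside them.

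**The effect may be small.** This stands in part. If nearly everyone clears before the cutoff, the median barely moves, and by 5 years the bias is close to nil.

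**Stronger readings.** A reader might infer that every clearance time will look too fast. The documents support this only for slow-clearing specimens at the primary analysis, and for PBMC the Week 20 start can push the other way. A reader might infer that PBMC peaks are wrong in general. They are not: peaks in participants sampled from the start are valid, and substudy members have 2 to 72 hour samples. A reader might also infer that in-study precautions are affected. Protocol 5.1 and Appendix 4 tie these to each participant's own consecutive negative samples, so the pooled table plays no part.

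**Conclusion.** The point holds in two limited parts.

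First, without a censoring rule the clearance summary at the primary analysis is biased short for specimens that many participants have not yet cleared. In the main illustration the median is short by about 1 week or less at true medians of 20 to 34 weeks, about 5 weeks at 52 and about 17 at 78. Other assumed distributions give more or less. All of these rest on assumed clearance times and follow-up. Only PBMC clearance is described as prolonged, and no figure is given.

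Second, the pooled PBMC peak and time to peak in the Dosed population mix two sampling schemes. The sponsor's rationale relies on participants already dosed for peak data, but the SAP does not carry that restriction over. The size depends on how many participants were dosed after the change, which is not given.

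Shedding is a tertiary/exploratory, descriptive endpoint outside the gatekeeping sequence. No test, power or type I error is affected. The change is still worth making before the tables are produced, because the planned summary would misdescribe persistence where persistence is longest.

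**What to change.** In SAP 6.3.2:
- Estimate each clearance time by Kaplan-Meier per specimen type. Censor participants without three consecutive negatives at their last sample of that type. Report the median and quartiles with 95% CI beside the percentage cleared.
- Restrict PBMC peak and time to peak to participants with PBMC sampling from the first weeks, in line with the Amendment 9 rationale, and state n.
- Footnote the PBMC clearance table: for participants whose routine sampling began at Week 20, a negative cannot be recorded earlier.

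This is a standard procedure on data already planned, with no change to trial conduct. The cost is a smaller n in the PBMC peak table and longer reported clearance times. An upper quartile or median may be not estimable at the primary analysis for a slow-clearing specimen, and should be reported as such.
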